### **Specific Objectives**

- To document patient experience in the study of financial incentives.
- To document the experience of people accompanying patients with type 2 diabetes mellitus.
- To test the acceptability and clarity of instructional material used to promote behavioral change.
- To test the feasibility of reaching the proposed clinical goals (weight loss and glycated hemoglobin).
- To test the "sufficiency" of the incentive amount given to both the patient and the patient's companion, in order to promote behavioral changes.
- To explore the sustainability of the companion's participation for 9 months.
- To explore activities that could make the companion more effective in helping the patient manage his/her diabetes.
- To explore whether the patient is able to keep a daily record of the effort made in managing his/her diabetes.
- To evaluate the feasibility of packaging and implementing a future clinical trial, which will evaluate the impact of the use of monetary incentives in patients with type 2 diabetes mellitus.

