### **3.5 Outcomes**

At the end of the three months, a comparison will be made between the achievements in terms of (1) weight loss and (2) glycated hemoglobin to then assess through qualitative research whether the amount of money given was the right one to promote weight loss, the role of education in diabetes and the process assessment.

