### **Arm1: Individual Incentives**

Participants will be required to come every 2 weeks to measure their weight and to collect a blood sample for glucose measurement with a glucometer. Weight will be measured in fasting conditions, using the same scale and at the same time as the previous visit.

Each participant will attend a total of 8 sessions (including the initial meeting). In sessions 2 to 7 the diabetes educator will weigh them to see if they reached the goal.

- ***If they reached the goal:*** They will be rewarded and asked about the actions taken to reach their goal. In addition, suggestions for improving their nutrition and diabetes management will be reviewed. For this purpose, the information entered by the participants in their diary will be used. They will also be asked about their physical activity, adherence to treatment and changes in their eating habits. If they have received a reward in the previous session, they will be asked about how they used that reward.

- **If they did not reach the goal:** They will be asked about the actions they took to lose weight and the main challenges in implementing them. For this purpose, the information entered by the participants in their diary will be used. Suggestions for improving their nutrition and diabetes management will be reviewed. They will also be asked about their physical activity, adherence to treatment and changes in their eating habits.
- The patient will fill out a diabetes self-management questionnaire at each session (See Annex 4).

In session 7, a blood sample will be collected to measure his/her Hba1c. The results will be given in session 8 (last session) in which he/she will be rewarded if his/her Hba1c has dropped at least 1% since the beginning of the study (See Annex 7).

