### 5.8. Analysis Plan

#### 5.8.1. Baseline and Follow-up

The information collected will be entered and tabulated in order to identify the participants' characteristics. Subsequently, the data will be descriptively analyzed using measures of central tendency, measures of dispersion, absolute frequencies and relative frequencies, according to the type of variable.

For longitudinal data analysis, the three arms of the study (individual incentives, mixed incentives set up by researchers, mixed incentives set up by participants) will be compared, using as outcomes the difference in weight (every 15 days for three months) and the difference in the percentage of glycated hemoglobin (at three months). For this purpose, relative risks with 95% confidence intervals will be used.

5.8.2. Qualitative Research: In-depth interviews. The interviews will be recorded in mp3, transcribed and then analyzed using Atlas-ti software. This software allows coding the interviews in order to identify common themes, frequency of opinions and explanatory details of the answers given.

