## **5.9. Protocol compliance**

This research study will be carried out in accordance with the protocol and good clinical practices. The protocol will not be amended without prior written approval by the Ethics Committee. All amendments will be submitted for evaluation to institutional ethics committees prior to their implementation, except when it is necessary to protect the participants' security, rights or welfare, or to eliminate immediate risks to them.

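### The only planned between-arm measure is a relative risk, but both named outcomes are continuous changes and no event is defined

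*Combined protocol and SAP*

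**What the plan says.** Section 5.8.1 (Baseline and Follow-up) holds the whole quantitative analysis plan, and it has two parts.

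- **Descriptive.** "the data will be descriptively analyzed using measures of central tendency, measures of dispersion, absolute frequencies and relative frequencies", according to the type of variable.
- **Comparative.** The three arms are compared "using as outcomes the difference in weight (every 15 days for three months) and the difference in the percentage of glycated hemoglobin", the latter at three months. The next sentence gives the method: "For this purpose, relative risks with 95% confidence intervals will be used".

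Other sections bear on what an event might be:

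- Section 3.5 Outcomes: "At the end of the three months, a comparison will be made between the achievements" in weight loss and HbA1c. It gives no threshold and no effect measure.
- Specific Objectives: one aim is "To test the feasibility of reaching the proposed clinical goals (weight loss and glycated hemoglobin").
- Section 3.6.2, Arm 1: "In sessions 2 to 7 the diabetes educator will weigh them to see if they reached the goal". Arms 2 and 3 weigh patients on the same schedule and likewise separate those who reached the goal from those who did not.
- Section 3.6.2, Arm 1, last session: "he/she will be rewarded if his/her Hba1c has dropped at least 1% since the beginning of the study". Arms 2 and 3 add a condition about the companion.
- Section 3.5 Intervention sets the fortnightly weight reward at a loss of one kilogram in two weeks.

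The 1 kg and 1% thresholds appear only as rules for paying the reward. No section makes either an analysis endpoint.

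**The concern.** A relative risk is a ratio of two proportions and is not defined for a change in kilograms or in HbA1c percentage. Before it can be computed, someone must turn each outcome into a yes/no event, and the plan does not say how.

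Three things are at stake.

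- The comparison cannot be carried out as written, and it is the only one planned. The descriptive means and dispersions are not a between-arm contrast with an interval.
- With no event fixed in advance, it could be chosen after the data are seen, and for weight different choices give different ratios.
- Section 2 says the results will be used to design a randomised trial. For the two outcomes named, the direct estimate is a between-arm mean difference with its confidence interval, and that is absent.

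**Working it through.** **Inputs from the documents.** 45 patients, 15 per arm (Section 3.4; 3 × 15 = 45, plus 2 × 15 = 30 companions, gives the stated 75). 95% intervals (Section 5.8.1). There is no power-based figure to reproduce.

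**Assumptions.** The documents give no attainment rate, SD, distribution or baseline correlation. All such values below are assumed and shown as ranges.

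**Step 1. Does the goal-attainment reading supply the missing event?**

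- *HbA1c:* nearly. There is one candidate, a drop of at least 1%, from the sample taken at session 7. What is missing is a sentence adopting it and saying whether 1% is absolute or relative.
- *Weight:* no. Section 3.5 Outcomes points to the end of three months and Section 5.8.1 to every 15 days. Per-visit, cumulative and end-of-study success are different events. Under the arm descriptions a patient has up to six goal weigh-ins (sessions 2 to 7), and no method is given for these correlated results. Section 3.5 Intervention counts seven follow-up sessions plus a final one, so the number of visits also needs reconciling.

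**Step 2. Does the choice of cut-off matter?** Take a normal outcome and a 1-SD shift between two arms. With reference-arm attainment p, the other arm's attainment is 1 − Φ(z − 1), where z = Φ⁻¹(1 − p).

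| Reference-arm attainment | Other arm | RR |
|---|---|---|
| 10% | 38.9% | 3.89 |
| 20% | 56.3% | 2.81 |
| 30% | 68.3% | 2.28 |
| 50% | 84.1% | 1.68 |

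The same shift gives ratios from 1.68 to 3.89.

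**Step 3. Information kept if attainment stands in for the mean.** Efficiency = f(c)² × Var / [p(1 − p)], where f(c) is the density at the cut-off c.

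| Attainment p | Normal | Logistic | t, 5 df | Double exponential |
|---|---|---|---|---|
| 50% | 0.637 | 0.822 | 0.961 | 2.0 |
| 30% | 0.576 | 0.691 | 0.795 | 0.857 |
| 20% | 0.490 | 0.526 | 0.588 | 0.500 |
| 10% | 0.342 | 0.296 | 0.305 | 0.222 |

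Loss is 1 − efficiency. At 30% it is 42%, 31%, about 21% and 14%. At 10% it is 66% to 78%. At 50% it runs from 36% (normal) to none (double exponential).

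**Step 4. Precision of a relative risk, 15 v 15, true RR 1.** SE(log RR) = √[2(1 − p)/(15p)]; interval = exp(±1.96 × SE).

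| p | SE | 95% interval |
|---|---|---|
| 50% | 0.365 | 0.49 to 2.05 |
| 30% | 0.558 | 0.34 to 2.98 |
| 20% | 0.730 | 0.24 to 4.18 |
| 10% | 1.095 | 0.12 to 8.56 |

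**Step 5. Precision of a mean difference.**

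- Unadjusted: t(0.975, 28 df) × √(2/15) = 2.048 × 0.365 = 0.75 SD.
- ANCOVA over three arms, complete data, 45 − 4 = 41 df, equal baseline and follow-up variances: the residual SD relative to the SD of change is √[(1 − r²)/(2(1 − r))] = √[(1 + r)/2]. The half-width is 2.020 × 0.365 × √[(1 + r)/2], which is 0.64, 0.68 and 0.72 SD of change at r = 0.5, 0.7 and 0.9. Chance baseline imbalance changes these very little (simulated means 0.641, 0.684, 0.722).

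**Step 6. Arms with no events.** P(none in an arm) = (1 − p)^15 = 0.0047, 0.0352 and 0.2059 at 30%, 20% and 10%. P(at least one of three arms with none) = 1 − [1 − (1 − p)^15]³ = 1%, 10% and 50%. When this happens, the usual RR and interval fail for at least two of the three pairs. Section 3.3.1 sets no minimum baseline HbA1c, so low attainment of a 1% drop cannot be ruled out.

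**The case against.** The best defence is that goal attainment is what the authors meant. Rewards are paid on thresholds, an objective is to test whether the goals can be reached, and Section 3.5 Outcomes speaks of achievements. The fortnightly 1 kg rule also matches the 15-day interval in Section 5.8.1, so per-visit attainment is the most natural reading for weight. For such a pilot a relative risk of attainment is a legitimate contrast. On this view the plan lacks only a linking sentence, the information loss in Step 3 is beside the point, and putting mean differences first is a preference. The defence can add that both measures are imprecise at 15 per arm, and that the planned measures of dispersion already give SDs for a later trial.

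Much of this stands. The reading is plausible; if attainment is the target, Step 3 shows no loss; and neither measure gives a firm answer at this size. It does not rescue the sentence. Section 5.8.1 names the differences themselves as outcomes, and no text links the reward rules to the relative risk. Even the per-visit reading leaves up to six correlated results per patient without a method. In Arms 2 and 3 the HbA1c reward also depends on the companion, so being paid is not the same as reaching the goal. Mean differences are not an imported preference: they follow from the outcomes the section itself names.

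**Conclusion.** The concern holds. As written, the plan's only between-arm measure does not apply to its own outcomes, no event is defined, and no between-arm mean difference with an interval is planned. This is a mismatch between outcome and measure, not just missing detail.

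Its numerical size depends on values the documents do not give. The loss from replacing the mean by attainment runs from none to 78% over the assumed distributions and rates, so no single figure should be quoted. The more robust practical point is the risk of arms without events, which is small at 30% attainment and about even at 10%.

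It should be fixed, but the severity is modest. The Protocol Summary calls the study exploratory, Section 3.1 describes a feasibility pilot, and no hypothesis test is planned.

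**What to change.** In Section 5.8.1, replace the relative-risk sentence with the following:

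- **Main comparison:** baseline-adjusted between-arm mean differences with t-based 95% intervals for the three pairs of arms, by ANCOVA. Regress weight at the last scheduled weigh-in on arm and baseline weight, naming the session, and three-month HbA1c on arm and baseline HbA1c.
- **Optional:** a repeated-measures model over all weigh-ins, with a covariance structure that lets the variance change over time.
- **Secondary:** relative risks with 95% intervals for explicitly defined goal attainment. State the event (including whether the 1% HbA1c drop is absolute or relative), the time point and the reference arm. If weight attainment is analysed per visit, account for within-patient correlation.

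The session counts in Section 3.5 Intervention and Section 3.6.2 should be reconciled so that the last weigh-in is unambiguous.

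The cost is a few lines of text and one amendment. Section 5.9 requires approval first: "The protocol will not be amended without prior written approval by the Ethics Committee". No new data, visits or patients are needed.

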## **5.9. Protocol compliance**

This research study will be carried out in accordance with the protocol and good clinical practices. The protocol will not be amended without prior written approval by the Ethics Committee. All amendments will be submitted for evaluation to institutional ethics committees prior to their implementation, except when it is necessary to protect the participants' security, rights or welfare, or to eliminate immediate risks to them.

## **5.10. Data security plan**

Data management will follow standards of good clinical practice. We will follow standard procedures and definitions for the evaluation and reporting of adverse events. The Principal Investigator will be responsible for reporting all adverse events that are observed or reported during the study. All study personnel will be instructed to detect and report any adverse events. The Principal Investigator will be responsible for centralizing all this information.

